- Knows HIV status (Screened AYA who do not know their HIV status will receive information on free voluntary HIV counseling and testing services)
- Living with HIV
- Has been prescribed medication to treat HIV
- Not attending school for learners with special needs (e.g., School of Skills)
- Has not repeated a grade in school more than once
- Have a smartphone that can download apps
- Feels comfortable using an app with content in English
- No plan to move outside of Cape Town in the next six months

- Have not previously participated in the MASi app testing phase of our study

Participants who meet these criteria will be invited for an in-person appointment. After completing the informed consent/assent process (including consent from an adult, if applicable), we will confirm the final eligibility criteria:

- Able to successfully install the MASi app on their smartphone

Eligible participants will complete a baseline assessment, which will be an interviewer-administered survey with data entered electronically by the interviewer using REDCap data collection software. Paper surveys will be available in the event online data entry is not possible. For survey questions with a higher potential for social desirability bias (e.g., sexual behavior and study feedback), we may offer participants the opportunity to self-enter data into REDCap.

Following the baseline assessment, the interviewer will use REDCap's randomization tool to assign participants to condition. Using this process, participants will be randomized to the intervention or control condition (1:1), with randomization stratified by gender. The intervention condition will include all features of *MASi* while the control condition will be an information-only version of *MASi* which will include the Resources feature and homepage. Study participants will be asked to engage with the app for 6 months. All participants will receive 1G in monthly cellphone data packages for 6 months; research staff will touch base with participants each month to ensure the participant still has access to a working device before sending data.

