Participants will complete follow-up assessments as well as 3- and 6-months follow-up. Assessments will take approximately 60 minutes and will be conducted in a private room so that participants can speak without being overheard. Phone assessments may be conducted in the event it is not possible to conduct in-person data collection. Assessments will include questions about assessing demographics, HIV-related knowledge, social support, loneliness, resilience, anxiety, depression, stigma, disclosure concerns, disclosure intentions, treatment adherence, sexual activity, perceived usability of *MASI*, and participant feedback about the study overall.

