## Statistical Analysis Plan

The study will enroll 50 adolescents and young adults with HIV into the study (25 males and 25 females based on self-reported sex assigned at birth). The study's sample size ( $n = 50$ ) was selected to be large enough to reasonably evaluate the feasibility and acceptability of MASi while balancing budgetary constraints.

Descriptive summaries will be computed for all study outcomes with continuous variables summarized with means and standard deviations (or medians with interquartile range in the case of skewed distribution) and categorical variables summarized with counts and proportions. Outcomes will be summarized, stratified by treatment group, at each available study time point.

As a pilot study with a primary focus on feasibility and acceptability, the examination of MASi's preliminary efficacy will be exploratory. To explore MASi's preliminary efficacy on ART adherence and social support at 3- and 6-months, we will use linear mixed models to compare outcomes among participants randomized to MASi compared vs. the information-only control at each time point. Log transformed outcomes and alternative modeling approaches such as Poisson and negative binomial will be considered in the event that assumptions for the linear model are violated. All models will include a fixed effect for sex assigned at birth (stratification variable) and a random intercept term to account for correlation in the response due to repeated measures within study participants over time. A random slope for participant will also be considered, as will the covariance structure of the errors (e.g., exchangeable, autoregressive). Distribution of residuals will be examined to confirm that modeling assumptions are met. Because sample size is small (this study is not powered to detect clinically meaningful effect sizes) and the regression analyses are exploratory in nature, inference will focus on the size and direction of the total treatment effects rather than statistical significance.

Additional exploratory analyses will examine MASi's effects over time on HIV/AIDS knowledge and stigma using methods similar to those employed for adherence and social support outcomes. We will also conduct descriptive analyses examining trends and patterns in user engagement with various components of the MASi interface over time.

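### The required terms of the efficacy models do not use the baseline value of each outcome, so the 3- and 6-month arm comparisons can be less precise than the planned data allow

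*Combined protocol and SAP*

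**What the plan says.** The SAP describes the efficacy analysis of ART adherence and social support in one paragraph. Linear mixed models will "compare outcomes among participants randomized to MASi compared vs. the information-only control at each time point", the follow-up times being 3 and 6 months. On model content: "All models will include a fixed effect for sex assigned at birth (stratification variable) and a random intercept term". It adds: "A random slope for participant will also be considered, as will the covariance structure of the errors (e.g., exchangeable, autoregressive"). If the linear model's assumptions fail, outcomes may be log transformed, and "alternative modeling approaches such as Poisson and negative binomial will be considered". On interpretation, "inference will focus on the size and direction of the total treatment effects rather than statistical significance". HIV/AIDS knowledge and stigma are to be analysed by similar methods, so they inherit the same description.

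The Aim 3 text of the protocol places baseline before allocation: "Following the baseline assessment, the interviewer will use" the REDCap randomisation tool. It then says "Participants will complete follow-up assessments as well as 3- and 6-months follow-up", and its list of assessment content includes "HIV-related knowledge, social support, loneliness, resilience, anxiety, depression, stigma, disclosure concerns, disclosure intentions, treatment adherence".

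No sentence says whether the baseline outcome is a covariate, a response with free arm means, a response with arm means constrained equal, part of a change score, or unused.

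**The concern.** A value measured before randomisation can be used to sharpen a later arm comparison. It is easy to assume that a random intercept already does this, because it links a participant's visits. It does not do so when each arm has its own mean at every visit, baseline included. The baseline data then only estimate the baseline means, and with complete data the follow-up contrast is the raw difference between arms.

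The SAP will read the magnitude and sign of effects from about 25 participants per arm and sets significance aside. The precision of those estimates is therefore the main thing this exploratory analysis delivers. Several treatments of baseline are also left open and can give different estimates. Naming one in advance removes a choice that could otherwise be made after seeing the data.

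**Working it through.** **Inputs.** N = 50 (SAP) and 1:1 allocation (protocol, Aim 3) give 25 per arm. Visits are baseline, 3 and 6 months, and sex is in the model. The plan has no figure of its own to reproduce, because the sample size was set by feasibility and budget, with no SD, effect size or power. Assumed: a linear model, equal SD at each visit, and a baseline to follow-up correlation rho of 0.3, 0.5 or 0.7, since the documents give no value. SEs are in SD units.

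**Formulas, complete data.**

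- Free arm means at every visit, or baseline unused: √(2/25) = 0.283 at every rho.
- Arm means constrained equal at baseline: √(2/25) × √(1 − rho²).
- Baseline as a covariate: √(2/25) × √((1 − rho²) × 46/45). The factor (N − 4)/(N − 5) is the cost of estimating one more coefficient.
- Change from baseline: √(2/25) × √(2(1 − rho)).

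| SE, exchangeable correlation | rho 0.3 | rho 0.5 | rho 0.7 |
|---|---|---|---|
| Free means or baseline unused | 0.283 | 0.283 | 0.283 |
| Constrained equal at baseline | 0.270 | 0.245 | 0.202 |
| Baseline as covariate | 0.273 | 0.248 | 0.204 |
| Change from baseline | 0.335 | 0.283 | 0.219 |

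Relative to 0.283, the constrained SE is 5%, 13% and 29% smaller. Generalised least squares over the three visits gives the same free and constrained values. A simulation with the variance components estimated by REML (10,000 trials per setting) gave an SD of the 6-month estimate, free against constrained, of 0.282/0.271, 0.282/0.246 and 0.285/0.202. At rho 0 it was 0.281/0.281, so the constraint costs essentially nothing.

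**Half-widths.** With t = 2.01, free means give 2.01 × 0.283 = 0.57. The constrained model gives 0.54, 0.49 and 0.41.

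**Autoregressive decay.** With lag-1 correlation rho, the correlation between baseline and 6 months is rho². The constrained 6-month SE is 0.283 × √(1 − rho⁴) = 0.282, 0.274 and 0.247, a gain of 0.4%, 3% and 13%. The 3-month gain is unchanged.

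**Break-even for the covariate model only.** Setting (1 − rho²) × 46/45 = 1 gives rho = √(1/46) = 0.147. With 40 completers it is √(1/36) = 0.167. At rho 0 the covariate raises the SE to 0.286, about 1%. The constrained model has no such threshold: it gains at any rho above about zero.

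**Dropout.** The documents give no rate. Suppose 5 per arm are lost completely at random after baseline. Follow-up data alone give √(2/20) = 0.316. Free means give 0.313, 0.308 and 0.300, so the random intercept recovers a little. Constrained means give 0.302, 0.274 and 0.226.

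**Covariance options.** A random intercept, a random slope, their covariance and a residual variance are 4 parameters. Two response visits supply 3 distinct variances and covariances, so this model is not identified; three visits supply 6, and it is. A slope uncorrelated with the intercept has 3 parameters and is identified at two visits. Two visits give one correlation, so exchangeable and autoregressive errors cannot be told apart. Exchangeable errors added to a random intercept are redundant at two or three visits: 3 parameters describe one variance and one covariance.

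**The case against.** The best defence is that the SAP's sentence on required terms sets a minimum, and that a random slope and an autoregressive structure make most sense with three visits. Baseline is then probably already in the response, and if its arm means were constrained equal nothing would be lost. This stands in part. A reader might infer that the plan excludes baseline adjustment; the text leaves it unstated and does not exclude it. But no constraint is named, and fitting the listed terms with ordinary arm-by-visit effects gives the less precise contrast.

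A second defence is that the contrast may be change from baseline, since the SAP also speaks of effects over time. The visit-by-visit wording makes this less natural. If it is meant, the constrained model is still more precise at each rho shown.

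Third, the content of the baseline survey is inferred. The assessment list follows the sentence on follow-up visits and includes app usability and study feedback, which fit follow-up only. That adherence, social support, knowledge and stigma are also asked at baseline is a strong inference, not a stated fact.

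Fourth, the gain is small in practice: efficacy is exploratory and unpowered, feasibility and acceptability come first, and rho is unknown. This stands and limits the weight of the point.

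**Conclusion.** The point holds as a modest, nearly free improvement. The required terms do not adjust the follow-up comparisons for baseline. With complete data and free arm-by-visit means, a random intercept recovers none of the available precision. Under exchangeable correlation of 0.3 to 0.7 the avoidable excess is an SE of 0.283 against 0.270 to 0.202 SD; under autoregressive decay it is much smaller at 6 months. Intervals stay wide either way.

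Three stronger readings are not supported. A reader might infer that the estimates are biased; with complete data, or dropout completely at random, the loss is in precision only. The reverse cannot be promised either: if baseline is unused and dropout depends on it differently by arm, bias is possible. A reader might also take a correlation of about 0.15 as a general threshold, but it belongs to the covariate model alone. Finally, a reader might infer that two visits rule out any random slope; that is true only of a slope correlated with the intercept.

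All figures assume a linear model with equal SDs and do not carry over to Poisson or negative binomial models.

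**What to change.** State in the SAP how baseline enters each arm-comparison model.

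- **Preferred, for the linear or log-transformed model:** keep baseline, 3 and 6 months as the response with arm-by-visit terms, constrain the arm means to be equal at baseline, and report the 3- and 6-month arm differences. A random slope and autoregressive errors remain available. Exchangeable errors should be dropped as redundant with the random intercept.
- **Alternative:** take the 3- and 6-month values as the response with baseline as a fixed covariate. The sentence on random slopes and error covariance must then be rewritten, because two visits do not identify a slope correlated with the intercept and cannot separate exchangeable from autoregressive errors.
- **Poisson or negative binomial fallback:** include baseline as a covariate on a suitable scale, for example the log, or the log of the value plus one if zeros occur.

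Cost: about two sentences for the preferred route and a small edit to the covariance options, with essentially no loss of precision if baseline proves uninformative. The covariate route costs about 1% in SE in that case. Neither needs new data, provided that the baseline survey contains these outcomes; the SAP should confirm that it does.
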